2.1 General methods

All statistical analyses, including summary tables and data listings, will be performed using the SAS® system (Version 9.3 or higher). Confidence intervals (CIs) will be two-tailed and constructed at a confidence level of 95%. P values will be two-sided and performed at a significance level of 5%.

All study data including observed and derived variables (e.g., change from baseline, response status) used in the summaries of analyses will be presented in by-subject listings. In general, efficacy, safety, demography, subject characteristics, and treatment related variables will be presented using descriptive statistics. For categorical parameters, the number and percentage of subjects in each category will be presented. The denominator for percentage will be based on the number of observations at that time point (i.e. observed cases). For continuous parameters, descriptive statistics will include number of observations, mean, standard deviation (SD), median, and range. Graphs will be used as appropriate.

Any change made to the finalized statistical analysis plan (SAP) after database lock will be documented in the Clinical Study Report (CSR).

For the primary analysis, non-inferiority will only be demonstrated if the CI is entirely below 0.5 for both co-primary endpoints in both the ITT and PP populations. Similarly, superiority will only be demonstrated if the lower confidence limit is entirely below 0 for both co-primary endpoints in both the ITT and PP populations. Therefore no multiplicity adjustment for Type I error is required.

2.2 Analysis Populations

The following populations will be defined for analysis:

- **Safety population:** Includes all subjects who received any of the investigational products, based on the as treated principle (i.e. according to the treatment actually received).
- **Intention-to-treat (ITT) population:** Includes all subjects who were randomized and had a baseline [REDACTED] for both the upper and lower lips. All ITT analyses will be based on the as randomized principle (i.e. according to the treatment they were randomized to).
- **Per protocol (PP) population:** Includes all subjects in ITT who complete the Week 8 visit without any deviations considered to have substantial impact on the primary effectiveness outcome.

The primary efficacy analysis of non-inferiority will be performed both on the ITT and the PP analysis set. Secondary effectiveness and all safety evaluations will be performed based on the ITT and the safety population set, respectively.

2.3 Study subjects

2.3.1 Subject disposition

The number of subjects in each study population (i.e. Safety, ITT and PP) will be summarized. Study population variables will also be presented in a data listing.

The disposition of subjects will be presented by treatment group, and in total, including numbers of subjects that were:

- Screened
- Randomized
- Completed
- Withdrawn (overall and by reason for withdrawal)

All withdrawn subjects will be presented in a by-subject listing.

2.3.2 Protocol deviations

Protocol deviations will be presented in a by-subject listing. Major protocol deviations will be summarized by site and overall.

Depending on the seriousness of the deviation, subject might be excluded from the PP population, which shall be documented prior to database lock.

For this study, the protocol deviations that will exclude subjects from PP are identified (but not limited to) below:

- General
 - Treatment not given according to randomization scheme at initial or touch-up (if touch-up done) treatment
- Efficacy
 - Pre-treatment value missing for at least one lip
 - Any other deviation considered to have substantial impact on the primary effectiveness outcome
- Other
 - Any key inclusion/exclusion criteria not met (with the exception of the ≤ 21 FST V-VI who do not have to meet the Thin/Very thin lip criterion)
 - Use of any prohibited medications or procedures defined in study protocol between initial treatment and the Week 8 visit, that is considered to have a substantial impact on the primary effectiveness outcome

Deviations from the SAP will be documented in the CSR.

2.3.3 Demographic characteristics

Demographic endpoints, baseline assessments, and subject characteristics will be summarized overall and by treatment for the ITT populations.

The following demographic and baseline variables will be included:

- Age (years)
- Sex
- Race
- Ethnicity

- Fitzpatrick skin types (FST)
- Baseline [REDACTED] (assessed by the blinded evaluator and treating investigator)
- Baseline Upper Perioral Lines & Oral Commissures [REDACTED] (assessed by the blinded evaluator and treating investigator)

2.3.4 Medical and surgical history, prior and concomitant medication/procedures

All summaries will be done by treatment group based on the ITT population.

History of surgical events, medical conditions and any prior dermatological procedures or implants will be provided in a by-subject listing.

Prior (with stop dates prior to initial treatment) and concomitant medications (ongoing or with stop dates on or after initial treatment) for all randomized subjects will be provided in a by-subject listing. Prior and concomitant medications will be summarized using World Health Organization Drug Dictionary (WHO-DD) Anatomical-Therapeutic-Chemical (ATC) classification and preferred term (PT) for each treatment. The number and percent of subjects, and the number of drugs, will be summarized by ATC code. Concomitant medications that started due to an AE will be stated in indication.

2.4 Efficacy analysis

2.4.1 Datasets analyzed

The primary efficacy analysis of non-inferiority will be performed both on the ITT and the PP analysis set. Secondary efficacy will be performed based on the ITT population set.

2.4.2 Handling of missing data

Number of missing values will be summarized and reported as appropriate.

Missing data for the primary analysis [REDACTED] will be handled using the hot deck imputation method. Specifically, each missing value [REDACTED] at Week 8 (recipient) will be imputed with a non-missing (observed) value from a subject randomly selected from the same imputation class (donor). Imputation classes will be defined based on treatment group, FST (I-III, or IV-VI) and whether or not the subject met [REDACTED] criterion (Yes, No), [REDACTED]

[REDACTED] missing values will be imputed in a similar manner. Alternative imputation classes may be used if deemed necessary.

Impact of missing data on the primary analysis for Week 8 endpoint will be evaluated by performing sensitivity analysis based on the observed cases in the ITT population.

All other endpoints will be evaluated based on the observed cases in ITT, i.e. no imputations will be done.

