2.4.3 Primary efficacy analysis

[figure not shown]
The primary efficacy analysis is test of non-inferiority of *Restylane® Kysse* to control treatment in the ITT and PP analysis sets, using the confidence interval approach and a non-inferiority margin of 0.5 units. [REDACTED]

Difference between treatments means (control – *Restylane® Kysse*), and the corresponding 2-sided 95% CI, will be calculated and presented for each of the 2 co-primary endpoints using the Student's t-statistic.

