2.7 Determination of Sample Size

Accounting for approximately 15% drop-outs and non-evaluable subjects due to protocol deviations at week 8, a total of approximately 280 subjects will be randomized in the study. It is expected that the number of randomized subjects will be similar across the study sites.

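### A single random hot-deck draw analysed with an ordinary t interval leaves imputation uncertainty out of the primary ITT 95% CI

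*SAP*

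**What the plan says.** SAP section 2.4.2 states that missing data for the primary analysis "will be handled using the hot deck imputation method". Each missing Week 8 value "will be imputed with a non-missing (observed) value from a subject randomly selected from the same imputation class (donor", which is one random donor per missing value. The donor pools are described as follows: "Imputation classes will be defined based on treatment group, FST (I-III, or IV-VI) and whether or not the subject met" a criterion whose name is redacted. Other classes may be substituted if thought necessary.

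Section 2.4.3 forms the difference in means (control minus Kysse) in the ITT and PP sets with a margin of 0.5. The two-sided 95% CI "will be calculated and presented for each of the 2 co-primary endpoints using the Student's t-statistic". The visible text of these two sections gives no repeat imputation, variance correction or seed.

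Three other provisions bear on the point:

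- Section 2.1: "non-inferiority will only be demonstrated if the CI is entirely below 0.5 for both co-primary endpoints in both the ITT and PP populations".
- Section 2.2 on the PP set: "Includes all subjects in ITT who complete the Week 8 visit", subject to having no important deviation.
- Section 2.4.2 on robustness: the impact of missing data is examined by "performing sensitivity analysis based on the observed cases in the ITT population".

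**The concern.** A t interval computed on the filled-in data treats every imputed value as a fresh independent observation and uses the full randomized n. It therefore misses two sources of variance. The information on the missing subjects comes only from the observed ones, and the random choice of donors adds noise of its own. The printed standard error is then too small. Someone else running the same rule with another random stream would get another estimate and another interval.

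The ITT interval is one of the two primary results, and section 2.1 presents it as a 95% interval. What is at stake is whether that reported interval carries its stated confidence.

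**Working it through.** **Inputs from the SAP.** About 280 randomized 2:1, that is 187 and 93 (section 1.1.1). 234 evaluable, 156 + 78 (section 1.1.2). Margin 0.5 (section 2.4.3). Two-sided 95% CI (section 2.1). Section 2.7 gives the loss allowance: "Accounting for approximately 15% drop-outs and non-evaluable subjects due to protocol deviations at week 8".

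**The plan's own figure.** 234 / 0.85 = 275.3, so 276, against approximately 280 stated; this agrees. The 15% mixes drop-outs with deviation exclusions, so it is an upper value for missing Week 8 scores. No rate for missing scores alone is visible. I take m = 5%, 10% and 15% as assumptions.

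**Variance, change score donated, one class, missing completely at random (MCAR).** In an arm of n with r observed and k imputed values, the mean after a single random hot deck has variance s²/r + (k/n²)·s²·(1 − 1/r). The t interval uses s²/n. The ratio of true to nominal variance is close to R = 1/(1 − m) + m. The nominal SE is too small by 1 − 1/√R, and coverage is 2Φ(1.96/√R) − 1. Neither the outcome SD nor the margin enters.

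| m | R | SE too small by | Coverage |
|---|---|---|---|
| 5% | 1.053 + 0.05 = 1.103 | 4.8% | 93.8% |
| 10% | 1.111 + 0.10 = 1.211 | 9.1% | 92.5% |
| 15% | 1.176 + 0.15 = 1.326 | 13.2% | 91.1% |

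**Dependence on the draw, change score donated.** The SD of the estimate from the draw alone is √(m·(1/187 + 1/93)), which is 0.028, 0.040 and 0.049 outcome SDs. The CI half-width is 1.96·√(1/187 + 1/93) outcome SDs. The 95% range of the draw divided by that half-width is √m = 22%, 32% and 39%.

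**Simulation of coverage** (187 vs 93, MCAR, 10,000 to 12,000 runs per setting, three donor classes per arm). The redactions hide whether the change score or the Week 8 score is donated, so both were run. The second case assumes baseline/Week 8 SDs of 0.6/0.9, 0.5/1 and 1/1 and correlations of 0 to 0.7.

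| m | Change donated | Week 8 score donated |
|---|---|---|
| 5% | 93.7% | 93.6-95.0% |
| 10% | 92.4% | 91.9-94.1% |
| 15% | 90.9% | 91.2-93.3% |

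At 15% missing, Week 8 score donation leaves the nominal SE about 6-13% too small. A further simulation used one to four classes per arm, donors drawn with and without replacement, and normal or rounded scores. It gave 93.6-94.6% at 5% missing and 91.0-92.9% at 15%, with the higher values where the classes predict outcome. The observed-case interval covered 94.7-95.5%.

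**Effect on the decision.** With the true difference at the margin and observed cases standing in for PP, false non-inferiority for one endpoint was 2.3-4.5% for ITT alone. It was 1.6-2.4% when ITT and PP must both pass, against a nominal 2.5%. The further simulation gave 1.4-2.1% for the joint rule.

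**The case against.** Four points can be made for the plan.

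- **The decision is protected.** PP holds only Week 8 completers, so it should contain few or no imputed values, and the joint error stays within 2.5%. This stands: no inflation of trial-level type I error is shown.
- **The planned observed-case analysis already gives a sound interval.** Under MCAR with change scores donated, its width relative to the single hot deck is about 1/√(1 − m) = 1.026, 1.054 and 1.085. Multiple imputation gives 1.025, 1.054 and 1.083. This is true, and any gain from multiple imputation when missingness depends on the donor classes was not simulated. But a sensitivity analysis does not correct the primary interval. At 15% missing the hot-deck estimate is the less precise of the two (variance factor 1.326 against 1.176), yet it would be printed with the narrower interval.
- **The size rests on unseen inputs.** The missing rate, the donated quantity and the full class definition are not visible, and 15% is an upper value. This stands. At 5% missing the loss of coverage is between nil and 1.4 points.
- **Redaction.** A seed, a repetition rule or a variance correction could lie in the blacked-out text. This cannot be ruled out. The visible wording, one random donor followed by a t interval, nevertheless describes single imputation.

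**Conclusion.** The concern holds on the visible text. If a material fraction of Week 8 scores is missing, the reported ITT interval is not a 95% interval: coverage is about 91-93% at 15% missing, 92-94% at 10% and 94-95% at 5%, where most results lie near 94%. The point estimate also depends on an unrecorded random draw.

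These figures assume MCAR, 187 vs 93 subjects and the visible single-donor rule. The Week 8 score results also rest on assumed SDs and correlations. The defect lies in the reported ITT estimate and interval, not in the overall non-inferiority decision. It should be fixed, with medium confidence because of the redactions.

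The point concerns the randomized study that the SAP describes. The Protocol describes an open-label study of 50 to 60 subjects (section 4.1) with no imputation (section 10.6), where the issue does not arise.

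**What to change.** Keep the donor classes and repeat the hot deck as a proper multiple imputation, for example 50 approximate-Bayesian-bootstrap draws: resample the donors within each class, then draw the imputed values from that resample. Run the same t analysis on each completed data set and combine by Rubin's rules. State the number of imputations and the seed in the SAP before database lock. If a redacted passage already provides this, nothing further is needed.

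In simulation (50 imputations, change score donated, 2,500 runs, Monte Carlo SE 0.4-0.5 points) coverage was 95.3%, 95.1% and 94.2% at 5%, 10% and 15% missing. With 20 imputations it was 94.4-95.0% at 5% and 94.0-94.6% at 15%.

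The cost is one SAP paragraph, a few lines of SAS, and an ITT interval wider on average by 2.5%, 5.4% and 8.3% at the three missing rates. Sample size, margin, decision rule and the observed-case sensitivity analysis stay as they are.

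### The only missing-data sensitivity analysis visible in the SAP shares the hot-deck primary's assumption, so it cannot test robustness to informative drop-out that differs between arms

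*SAP*

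**What the plan says.** SAP 2.4.2 handles missing Week 8 primary values by hot deck: each one "will be imputed with a non-missing (observed) value from a subject randomly selected from the same imputation class (donor"). On the classes it says: "Imputation classes will be defined based on treatment group, FST (I-III, or IV-VI) and whether or not the subject met" a criterion whose name is redacted. It adds a discretionary option: "Alternative imputation classes may be used if deemed necessary".

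The check on this is one sentence, and it applies to ITT: "Impact of missing data on the primary analysis for Week 8 endpoint will be evaluated by performing sensitivity analysis based on the observed cases". No other missing-data sensitivity analysis for the primary endpoint appears in the visible text.

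SAP 2.4.3 tests non-inferiority on control minus Kysse "using the confidence interval approach and a non-inferiority margin of 0.5 units". SAP 2.1 requires the interval to lie below 0.5 for both co-primary endpoints in both ITT and PP. SAP 2.2 defines PP as the set that "Includes all subjects in ITT who complete the Week 8 visit without any deviations considered to have substantial impact on the primary effectiveness outcome". SAP 2.7 sets the randomized number at about 280: "Accounting for approximately 15% drop-outs and non-evaluable subjects due to protocol deviations at week 8".

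The protocol supplied describes a different, open-label study of 50 to 60 subjects. Its section 10.6 presents observed cases without imputation, so it adds no missing-data plan for this randomized comparison.

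**The concern.** A random draw from observed donors in a class has the observed class mean as its expected value. The observed-case analysis uses the same observed values without the fill-in. Both therefore assume that, within arm and class, subjects without a Week 8 value would have scored like those with one. If that is false in one arm, or to a different degree in the two arms, both estimates move the same way by nearly the same amount. PP does not break the link, because it contains only subjects who completed Week 8. Changing the classes would not break it either, because donors are still observed subjects.

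At stake is how agreement will be read. SAP 2.4.2 presents the comparison as the evaluation of the impact of missing data. If ITT hot deck, ITT observed cases and PP all fall below 0.5, a reader will take the claim as robust, although none of the three has varied the assumption that matters most for drop-outs. In a non-inferiority test, crediting Kysse drop-outs with the results of Kysse completers favours the claim if those drop-outs in truth did worse.

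**Working it through.** **The plan's own figure.** 234 evaluable / (1 − 0.15) = 275.3, so 276, which fits the stated approximate 280. With exactly 280, the implied loss is 1 − 234/280 = 16.4%. The 2:1 split gives about 187 and 93 randomized, 156 and 78 evaluable. The power calculation cannot be reproduced, because SD, assumed difference and power are not visible.

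**Inputs.** From the SAP: 187/93 subjects, margin 0.5, two-sided 95% Student's t interval, planned loss of 15%. Assumed: SD 1.0, the size of the shift in missing subjects, and, where classes are modelled, class shares of 70/22.5/7.5% with class means and missing rates.

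**1. Do the two analyses target the same estimate?** With class share w, missing rate m and observed class mean μ:

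- hot-deck arm mean = Σ wμ
- observed-case arm mean = Σ w(1 − m)μ / Σ w(1 − m)

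These are equal when m does not vary by class. The treatment differences also agree when class-dependent missingness and class means are the same in both arms. With Kysse missing 12/20/30% by class and control 15% throughout, the two differences are 0.012 apart. In an extreme opposite-direction case they are 0.061 apart. Both gaps are small against 0.5.

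**2. Bias shared by both.** If missing subjects are δ units worse than observed ones, each analysis estimates

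true difference − (m_K·δ_K − m_C·δ_C).

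- m = 0.15, δ_K = 1.0, δ_C = 0: 0.50 − 0.15 = 0.35. The shift is 0.15/0.5 = 30% of the margin.
- m = 0.05, same shift: 0.50 − 0.05 = 0.45.
- m = 0.15, δ = 1.0 in both arms: 0.50 − 0 = 0.50, no bias.

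**3. False non-inferiority per endpoint (true difference 0.5, only Kysse shifted by 1.0, 15% missing).** Simulated half-widths are 0.276 (observed cases) and 0.254 (hot deck); the estimates have SD 0.141 and 0.149.

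- Observed cases: the upper limit is below 0.5 if the estimate is below 0.224. z = (0.224 − 0.35)/0.141 = −0.89, about 19%.
- Hot deck: the threshold is 0.246. z = (0.246 − 0.35)/0.149 = −0.70, about 24%.

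Simulation gives 19% and 24% to 25%, against 2.5% nominal, and the two verdicts agree in about 91% of these trials. At 5% missing, the standard error is √(1/177.65 + 1/88.35) = 0.130 and the half-width about 0.256. Then z = (0.244 − 0.45)/0.130 = −1.58, about 6% for observed cases.

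**4. Joint rule.** Both co-primaries are placed at the margin, PP is approximated by observed cases, and the assumed endpoint correlation is 0.5 to 0.8. For the 1.0-unit shift at 15% missing the false-claim rate is about 7% to 11%. For a 0.5-unit shift it is about 2% to 4%. For a 1.0-unit shift at 5% missing it is about 1% to 3%.

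**5. What observed cases does show.** With ignorable missingness and a true difference of 0.5, the per-endpoint false rate is about 2.6% for observed cases and 4.2% to 4.6% for hot deck. The excess comes from treating single imputed values as real data, and observed cases exposes it.

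**6. Where a claim would tip.** With 156/78 evaluable and SD 1.0, the half-width is 1.970 × √(1/156 + 1/78) = 0.273. The tipping shift is (0.5 − observed difference − 0.273)/0.15.

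| Observed difference | Tipping shift (units) |
|---|---|
| 0 | 1.51 |
| 0.1 | 0.85 |
| 0.2 | 0.18 |

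With SD 0.8 the shifts are 1.88, 1.21 and 0.54. With SD 1.2 they are 1.15 and 0.48, and at 0.2 non-inferiority already fails.

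**The case against.** The strongest case on the other side has five parts.

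- **Not identical, not empty.** A reader might infer that the two analyses agree by construction and that the check carries no information. The documents do not support that. The classes use FST and a further criterion, so class-related drop-out can separate the estimates. If the redacted imputed quantity is the Week 8 score and not the change, baseline differences could add to the gap. Observed cases also has the wider interval and reveals dependence on single-imputation precision. This stands, and it limits the point to informative drop-out.
- **Joint decision rule.** A reader might take 19% to 25% as the chance of a false claim for the trial. It is a per-endpoint rate. SAP 2.1 needs both co-primaries in both sets, which brings it to about 7% to 11% with both endpoints at the margin. It nears the observed-case rate only if the other endpoint is well inside the margin. This stands.
- **The 15%.** It includes subjects with protocol deviations, who may have Week 8 data and need no imputation. Truly missing data may be fewer, and the bias shrinks in proportion. This stands.
- **Direction.** A reader might infer that Kysse drop-outs are expected to do worse than control drop-outs. No document says so, and equal shifts in both arms cancel. The 1.0-unit shift is twice the margin and is an illustration. This stands.
- **Redaction.** Text next to the imputation rule is blacked out, so the word only applies to the visible text. However, the sentence naming the sensitivity analysis is complete as printed.

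These parts reduce the size and narrow the wording. None of them supplies an analysis that varies the shared assumption.

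**Conclusion.** The point holds in limited form. In the visible SAP, hot deck, observed cases and PP all rest on missing subjects resembling observed ones in the same arm (for hot deck, the same arm and class). Agreement among them cannot show robustness to informative drop-out that differs between arms. The shared bias is the missing fraction times the shift in outcome: 0.15 units (30% of the margin) at 15% missing and a 1.0-unit shift in Kysse only, 0.05 units at 5% missing, and none if both arms shift equally.

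The SD, the shifts, the 5% figure and the endpoint correlation are assumptions, and 15% is an upper planning figure. The primary analysis can stand. What falls short is the stated evaluation of the impact of missing data, and the amendment is worthwhile because a claim could tip at a small shift if the observed difference is near 0.2.

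**What to change.** Add to SAP 2.4.2 a delta-adjusted tipping-point analysis for the primary endpoint:

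- Use multiple imputation within the stated classes, so that the interval reflects imputation uncertainty.
- Subtract increasing shifts from the imputed Kysse values, in steps of 0.25 units, leaving control imputations unchanged.
- Continue until the upper 95% limit reaches 0.5 for either co-primary or the scale limit is reached. A grid ending at 1.0 would be too short, since the tipping shift is about 1.5 units at an observed difference of 0 with SD 1.0.
- Report that shift together with the number missing per arm, so that readers can judge its plausibility.
- Keep observed cases as a supporting analysis.

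The cost is SAP wording, one extra program and one extra table; no new data are needed. The downside for the sponsor is that the table may show the claim to be fragile.
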